### 4.3 Primary Outcome Analysis

#### *Longitudinal Analysis (Main Approach):*

We will utilize **repeated measures analysis** to assess treatment effects on the continuous primary outcomes (PHQ-9, FSS, MMSE, BI) over time. A linear mixed-effects model (LMM) will be fitted for each outcome with fixed effects for treatment group (intervention vs control), time (categorical: baseline, 1m, 3m, 6m), and the group  $\times$  time interaction. Each model will include a random intercept for each participant to account for within-subject correlations over time (assuming an unstructured covariance or other appropriate structure based on model fit). The primary parameter of interest is the group  $\times$  time interaction term at 6 months, which tests whether the change from baseline to 6 months differs between groups. If this interaction is significant ( $p < 0.05$ ), it indicates a differential treatment effect over time. We will report the estimated mean change from baseline to 6 months in each group and the difference in change between groups (with 95% CI and p-value). For reference, we will also report group differences at intermediate time points (1 and 3 months) from the same model, though these are secondary.

Assumptions of the LMM (normality of residuals, etc.) will be checked. If necessary (e.g., for skewed distributions like FSS), we may apply transformations (e.g., log transform) or use a nonparametric approach. However, given our sample size, the LMM with robust standard errors should be adequate even if mild deviations exist.

As an alternative verification, we may perform a **GEE analysis** for each outcome. The GEE will treat time as a repeated factor and use an exchangeable working correlation to account for repeated measures. GEE provides population-averaged estimates and is robust to misspecification of correlation. The results from GEE (in terms of intervention effect over time) will be compared to the LMM results. We anticipate they should converge, but any discrepancies will be examined (e.g., if dropout patterns influence results differently).

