### 3. Outcomes and Endpoint Definitions

#### Primary Efficacy Outcomes:

- **Depression Severity:** Change in Patient Health Questionnaire-9 (PHQ-9) score from baseline to follow-ups. The PHQ-9 is a 9-item scale (0–27 range); higher scores indicate worse depressive symptoms. The primary comparison will be the difference in mean PHQ-9 change from baseline to 6 months between groups. Additionally, trajectories over all time points will be considered. We will also examine the proportion of participants in each group achieving remission of depression (PHQ-9 < 5, for example) at 6 months as a supportive outcome.

- **Fatigue Level:** Change in Fatigue Severity Scale (FSS) score (range 9–63, higher = more fatigue). Same approach as PHQ-9: continuous score change and possibly categorization (e.g., FSS  $\geq 36$  indicating significant fatigue) for supplementary analysis.

- **Cognitive Function:** Change in Mini-Mental State Examination (MMSE) score (0–30, higher = better cognitive function). We will consider the mean change and group differences; additionally, the proportion of participants with cognitive impairment (MMSE  $\leq 24$ ) at each time point will be noted.

- **Physical Functional Independence:** Change in Barthel Index (BI) score (0–100, higher = more independent). Primary focus on mean score change at 6 months. Also, we may categorize outcomes (e.g., BI  $\geq 90$  as independent vs <90) for descriptive comparison.

Each of these primary outcomes will be analyzed as a continuous variable using appropriate parametric or nonparametric methods as outlined in Section 4. The primary time horizon for efficacy is the 6-month post-intervention assessment, though intermediate time points will be analyzed to observe trends.

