#### *Endpoint Analysis (Supportive):*

We will also analyze the **6-month endpoint directly** using analysis of covariance (ANCOVA) or t-tests. For each outcome, an ANCOVA will be conducted with the 6-month score as the dependent variable, treatment group as factor, and baseline score of that outcome as a covariate. This is a common approach to improve precision. The estimated group effect from ANCOVA (difference in 6-month mean outcomes adjusted for baseline) will be reported with 95% CI. Alternatively, we may compare the change scores (6-month minus baseline) between groups via an independent-samples t-test (equivalent to ANCOVA under equal baseline means). Both approaches yield the treatment effect estimate; ANCOVA is preferred if there were any baseline imbalances in that outcome.

Additionally, within-group changes from baseline will be assessed using paired t-tests for descriptive context (e.g., PHQ-9 reduction in intervention group, p-value; in control group, p-value). These within-group tests will not be used to infer treatment efficacy but to illustrate magnitude of change.

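### The primary mixed model lets each arm have its own baseline mean, so its 6-month test is the valid but usually less precise change-score comparison, and its covariance and standard error are not fixed

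*SAP*

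**What the plan says.** SAP 4.3 (Longitudinal Analysis) describes a linear mixed model that "will be fitted for each outcome with fixed effects for treatment group (intervention vs control), time (categorical: baseline, 1m, 3m, 6m"), together with the group-by-time interaction and a participant random intercept. The key parameter is the 6-month interaction, "which tests whether the change from baseline to 6 months differs between groups". This agrees with SAP 3, "The primary comparison will be the difference in mean PHQ-9 change from baseline to 6 months between groups", and with the protocol's sample-size section, which is based on mean PHQ-9 change.

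On the covariance, the random-intercept sentence adds "assuming an unstructured covariance or other appropriate structure based on model fit". On standard errors, the only statement is that "the LMM with robust standard errors should be adequate even if mild deviations exist".

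Baseline adjustment appears under Endpoint Analysis (Supportive), as an ANCOVA of the 6-month score. The SAP says of it: "This is a common approach to improve precision". The same paragraph offers a comparison of change scores "between groups via an independent-samples t-test (equivalent to ANCOVA under equal baseline means") and adds that "ANCOVA is preferred if there were any baseline imbalances in that outcome". SAP 4.2 leaves open adjusting the primary model if baseline comparisons show a clear need, without defining that need.

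The protocol's Schedule of Events places randomisation after the baseline assessments.

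**The concern.** Because baseline is one of the four outcome times and group has its own main effect, each arm's baseline mean is estimated separately. The 6-month contrast then subtracts the full observed baseline difference between arms. In a randomised trial with a pre-randomisation baseline, that difference is pure sampling error. A model with one common baseline mean subtracts only the share of it that predicts the 6-month score. It targets the same treatment effect, usually with a narrower interval.

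Two further points concern the same analysis.

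1. **Covariance and standard error.** A single random intercept has one variance, so it has no unstructured form. No rule is given for choosing another structure, and robust standard errors are mentioned but not prescribed. Two analysts following the text could report different p-values for the headline test. A random intercept with independent residuals implies equal correlation between all pairs of visits. If correlation falls with time, its model-based standard error for the longest gap, baseline to 6 months, is too small.
2. **The equivalence remark.** With equal observed baseline means, the change-score t-test and ANCOVA share a point estimate, but not a standard error, interval or p-value. Precision is therefore a reason to use ANCOVA whether or not the arms look imbalanced.

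**Working it through.** **Inputs.** From the protocol's sample-size section: difference 3.43, SD 5.5 (read as the SD of change), two-sided 0.05, power 0.80, minimum 43 per arm, 46 planned. The documents give neither the baseline-to-6-month correlation ρ nor SDs for FSS, MMSE or the Barthel Index. So ρ = 0.3, 0.5 and 0.7 are assumptions, and the sizes below are for PHQ-9 only.

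**The plan's own figure.** n per arm = 2 × [5.5 × (1.960 + 0.842) / 3.43]² = 40.4, so 41; with the t distribution, 42. The stated 43 is reproduced within 2. At 46 per arm the change-score test has 84.1% power (noncentral t, 90 df), and the 95% CI half-width is 2.28 points.

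**What the primary model estimates.** In 150 simulated trials with complete data, the 6-month interaction equalled the simple difference in mean change to within 3 × 10⁻¹⁴. Its mean was −3.43 against a true −3.43. There is no bias.

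**Gain from a common baseline.** With 6-month SD = k × baseline SD,

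variance ratio (adjusted / change score) = k²(1 − ρ²) / (1 + k² − 2ρk),

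which is (1 + ρ)/2 when k = 1. Multiplying the SD of 5.5 by the square root of this ratio gives, at 46 per arm (89 df):

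| k | Variance ratio, ρ = 0.3/0.5/0.7 | Power, % | CI half-width |
|---|---|---|---|
| Change score | 1 | 84.1 | 2.28 |
| 1 | 0.65/0.75/0.85 | 95.6/92.7/89.4 | 1.84/1.97/2.10 |
| 1.25 | 0.78/0.89/0.98 | 91.6/87.9/84.8 | 2.02/2.15/2.26 |
| 1.5 | 0.87/0.96/1.00 | 88.7/85.4/84.2 | 2.13/2.24/2.28 |

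The gain vanishes as the slope of the 6-month score on baseline, ρk, approaches 1.

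**The proposed four-visit model.** This was simulated with 2,000 trials per setting, visits at months 0, 1, 3 and 6, correlation ρ^(months apart/6), k = 1 and unstructured residuals fitted by REML. Three participants per arm drop out (46 − 43), one of them with no follow-up visit.

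| Model | Power, % (ρ = 0.3/0.5/0.7) | Half-width | Type I error, % |
|---|---|---|---|
| Common baseline | 95.0/90.9/87.8 | 1.88/2.01/2.15 | 4.9/4.5/5.4 |
| Free baseline | 81.9/82.5/82.1 | 2.32/2.33/2.33 | 5.2/4.9/5.7 |

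**Random-intercept standard error.** With complete data and equal variances, the fitted residual variance is proportional to 1 − r̄, where r̄ is the mean of the six pairwise correlations. The true variance of the contrast is proportional to 1 − ρ. Hence

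model SE / true SE = √[(1 − r̄)/(1 − ρ)].

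Under the same assumed decay with ρ = 0.5, the six correlations are 0.891, 0.794, 0.707, 0.707, 0.561 and 0.500, so r̄ = 0.693. The ratio is √(0.307/0.5) = 0.78, and the actual level is 2[1 − Φ(1.96 × 0.783)] = 12.5%.

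- For ρ = 0.3/0.5/0.7 the ratios are 0.81/0.78/0.77 and the levels 11.3/12.5/13.4%. Simulation with 100,000 trials per setting gives 11.4/12.8/13.4%.
- If correlation at very short gaps is capped at 0.9 to allow for measurement error, the levels are 10.5/10.7/9.7%; capped at 0.8, they are 9.1/9.0/7.2%.
- Under constant correlation the ratio is 1 and the level 5%.
- With robust standard errors under full decay, the simulated level is 5.0/6.0/5.3%.

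**The case against.** The strongest reply is that the baseline point is a choice between two valid analyses. Sample size, primary comparison, model contrast and effect size are all on the change scale, and planned power is met (84% against 80%). ANCOVA estimates are already planned as supportive. The size of the gain rests on correlations and SD ratios that the documents do not give, and at k = 1.5 and ρ = 0.7 there is none. All of this stands, and it is why the baseline point is one of precision only. It does not remove the case for the change: the baseline scores are already collected, and the supportive ANCOVA is neither primary nor firm, because a t-test is offered in its place.

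On the covariance, the SAP wording can be read as an unstructured residual covariance across visits, and inflation needs an analyst to use neither that nor robust standard errors. That is fair: the fault is ambiguity, not a planned wrong standard error. The 11 to 13% also assumes pure decay; allowing for measurement error brings it to roughly 7 to 11%. Those levels still matter for a test at 5%, and the text as written permits them.

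**Conclusion.** The concern holds. The primary contrast is unbiased and planned power is intact, but the model does not use the fact that the arms share a baseline mean. For PHQ-9 with equal SDs and ρ from 0.3 to 0.7, a common baseline narrows the 95% CI half-width from 2.28 to between 1.84 and 2.10 points and raises power from 84% to between 96% and 89%. The gain is smaller when the 6-month SD exceeds the baseline SD. No figure can be given for the other three primary outcomes.

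The unfixed covariance and standard error are the part that can affect validity. The inflation is conditional on a random-intercept model with model-based standard errors and correlation that decays over time. The equivalence remark is a minor wording error. The change should be made, but the primary analysis is not invalid without it.

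**What to change.** - **Primary model (SAP 4.3).** Use a constrained longitudinal model: four-level time, no group effect at baseline, and group by time at 1, 3 and 6 months. Everyone randomised with any data stays in, and the 6-month interaction remains the reported test.
- **Covariance and standard error.** Replace the random intercept with an unstructured residual covariance (4 visits, 10 parameters). State one standard-error and degrees-of-freedom method and a fallback order if the model does not converge. If the random intercept is kept, commit to robust standard errors; the common-baseline model needs them too (model SE 0.85/0.81/0.78 of the true SE under decay).
- **Supportive analysis.** Make it ANCOVA regardless of observed imbalance. Delete the change-score alternative, the equivalence remark and the imbalance condition.
- **SAP 4.2.** State that use of an outcome's own baseline score does not depend on the baseline comparisons.
- **SAP 4.4.** Apply the same model to the Stroke Impact Scale.

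The cost is wording in SAP 4.2 to 4.4 and a few lines of code. No new data are needed, and the sample size and estimand do not change. Cohen's d can stay on the SD of change, provided the report says which difference is its numerator. Make the change before clinical outcomes by arm are seen. SAP 1 says the plan precedes unlocking of the database, but SAP 4.5 refers to preliminary fNIRS results by group and time. If clinical outcomes by arm have also been seen, report the change as a deviation under SAP 5.

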#### *Endpoint Analysis (Supportive):*

We will also analyze the **6-month endpoint directly** using analysis of covariance (ANCOVA) or t-tests. For each outcome, an ANCOVA will be conducted with the 6-month score as the dependent variable, treatment group as factor, and baseline score of that outcome as a covariate. This is a common approach to improve precision. The estimated group effect from ANCOVA (difference in 6-month mean outcomes adjusted for baseline) will be reported with 95% CI. Alternatively, we may compare the change scores (6-month minus baseline) between groups via an independent-samples t-test (equivalent to ANCOVA under equal baseline means). Both approaches yield the treatment effect estimate; ANCOVA is preferred if there were any baseline imbalances in that outcome.

Additionally, within-group changes from baseline will be assessed using paired t-tests for descriptive context (e.g., PHQ-9 reduction in intervention group, p-value; in control group, p-value). These within-group tests will not be used to infer treatment efficacy but to illustrate magnitude of change.

### ***Effect Size:***

For each primary outcome at 6 months, we will compute **Cohen's d** effect size for the difference between intervention and control. This can be calculated as the difference in mean change scores (intervention minus control) divided by the pooled standard deviation of change. If using ANCOVA, we can compute an approximate effect size using the baseline-adjusted means. We will interpret effect sizes with standard benchmarks ( $d \approx 0.2$  small,  $0.5$  medium,  $0.8$  large). In addition, effect sizes for within-group change (e.g., baseline vs 6-month in intervention group) may be reported to gauge the magnitude of improvement in absolute terms. To provide confidence intervals for effect sizes, we will use a bootstrap technique: the dataset will be resampled (with replacement) 1000 times, the effect size computed for each resample, and the 2.5th and 97.5th percentiles will form the CI. This bootstrap CI is especially useful if normality assumptions for effect size are uncertain.

### ***Missing Data Handling:***

Missing data is expected primarily from dropouts (participants who miss the 6-month assessment, for example). The primary mixed-model analysis (LMM or GEE) can accommodate missing-at-random (MAR) data by using all available observations per participant without imputation. This is our main strategy for ITT analysis – using mixed models inherently includes participants with partial data. However, we will examine the pattern of missingness: if dropout is related to observed characteristics (e.g., those with worse baseline depression are more likely to drop out), the mixed model (assuming MAR conditional on those characteristics) should handle it; if we suspect data are not missing at random, we may perform a sensitivity analysis with imputation.

For sensitivity, we will perform a multiple imputation for missing 6-month outcomes. We will use a multiple imputation by chained equations (MICE) approach including baseline values, group, and available follow-up values to impute missing outcomes. Perhaps 20 imputations will be generated. The primary outcomes will then be analyzed on each imputed dataset and pooled results reported. We may also use a simpler Last Observation Carried Forward (LOCF) as a very conservative scenario (assuming no change after dropout) and re-run primary comparisons to see if conclusions change. The LOCF analysis will not be primary but provides a worst-case bound (especially if the control group has higher dropout, LOCF would bias toward no difference).

Participants who withdraw consent entirely or are lost to follow-up will not contribute post-dropout data; they remain in ITT (with whatever data available up to withdrawal). If a participant dies during the study (which is possible given stroke population), that is a competing risk; we will include them in analysis up until the point of death. If many deaths occur (expected to be low), we could consider a composite outcome or survival analysis for mortality, but given sample size we will likely just report any deaths separately.

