#### **4.6 Handling of Missing Data and Outliers**

As noted, the mixed models and GEE inherently handle missing longitudinal data under MAR. We will examine the extent of missingness at each follow-up. If  $> 10\%$  of data are missing for key outcomes, we will do multiple imputation as described (Section 4.3). We will also conduct a per-protocol analysis (excluding dropouts) for comparison. If ITT and PP results differ meaningfully, we will attempt to understand why (e.g., maybe dropouts in control differ in outcome).

**Outliers:** Before final analysis, data will be checked for any outlier values (e.g., a BI score that is impossible, or an extreme fNIRS value beyond physiological range). Any obvious data entry errors will be corrected (by checking source documents). Legitimate outliers will be kept in the analysis, but we may perform robustness checks by running analyses with and without outliers to see if results change. If a particular participant's data unduly influence a result (Cook's distance or residual diagnostics in regression), this will be reported.

For questionnaire scales, if an individual item is missing, we will handle per instrument guidelines (often prorating or mean substitution if  $\leq 1$  item missing on PHQ-9 or FSS, etc.), otherwise the score is set to missing.

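### The optional LOCF analysis is labelled a conservative worst case, which it is not, and no specified analysis otherwise allows for dropout that is not at random

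*SAP*

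**What the plan says.** The main analysis is a mixed model on all available observations, justified under missing at random (MAR). Under Missing Data Handling in SAP section 4.3, three further provisions follow.

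- If non-random missingness is suspected: "if we suspect data are not missing at random, we may perform a sensitivity analysis with imputation". No method is named.
- Multiple imputation is stated as a commitment: "For sensitivity, we will perform a multiple imputation for missing 6-month outcomes". It uses chained equations, an "approach including baseline values, group, and available follow-up values to impute missing outcomes".
- LOCF is optional and explicitly not primary. It is offered "as a very conservative scenario (assuming no change after dropout") and is said to be useful because it "provides a worst-case bound (especially if the control group has higher dropout, LOCF would bias toward no difference").

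SAP section 4.6 returns to imputation with a threshold. If more than 10% "of data are missing for key outcomes, we will do multiple imputation as described (Section 4.3"). It then adds: "We will also conduct a per-protocol analysis (excluding dropouts) for comparison". The supportive endpoint analysis in 4.3 is an ANCOVA on the 6-month score; alternatively, "we may compare the change scores (6-month minus baseline) between groups via an independent-samples t-test".

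**The concern.** The SAP claims two properties for LOCF: that it leans toward no difference, most of all when control dropout is higher, and that it marks a worst case. If either fails, agreement between LOCF and the primary result would be reported as surviving a severe test that was never applied.

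This matters more because LOCF is the only listed analysis that departs from MAR at all, and it does so through one fixed assumption of no change after dropout. The trial is open-label, the outcome assessor is unblinded, and only one arm has therapist contact (Protocol, Study Design and the blinding section). Dropout for different reasons in the two arms is therefore plausible.

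**Working it through.** **Inputs from the documents.** Protocol, Sample Size: difference 3.43 PHQ-9 points, SD 5.5, two-sided α 0.05, power 0.80, 43 needed and 46 enrolled per group. Visits are at baseline and 1, 3 and 6 months. The plan's figure reproduces closely: 2·(5.5·(1.960+0.842)/3.43)² = 40.4, so 41 by the normal formula and 42 with the t distribution, against the stated 43. The implied attrition allowance is 3/46 = 6.5%; no rate is stated. With 46 per arm, SE = 5.5·√(2/46) = 1.147.

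**Assumed, because the documents give no figure.** Control improvement Dc of 1–4 points; f = 0.25 if the last visit is month 1 and 0.625 if it is month 3; dropout by arm as shown.

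**1. Direction of the bias.** If dropouts would have had their arm's mean change, the LOCF mean improvement in an arm is (1−d)D + d·f·D = D − d(1−f)D. Subtracting control from intervention, and then the truth, gives

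bias in favour of the intervention = (1−f)(dc·Dc − di·Di), with Di = Dc + effect.

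Raising dc raises the bias whenever Dc > 0.

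| Case | Dropout, control vs intervention | Bias (PHQ-9 points) |
|---|---|---|
| No effect | 15–20% vs 5% | +0.04 to +0.45 |
| No effect | 4/46 vs 2/46, or 5/46 vs 1/46 | +0.02 to +0.26 |
| No effect | 3/46 vs 3/46 | 0 |
| Effect 3.43 | 3/46 vs 3/46 | −0.17 (f = 0.25) or −0.08 (f = 0.625) |
| Effect 3.43 | 15–20% vs 5% | −0.05 to +0.32 |

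The ends of the first row are 0.375 × 0.10 × 1 = 0.04 and 0.75 × 0.15 × 4 = 0.45, the latter being 0.39 SE. The chance of a false significant result in favour of the intervention is 1 − Φ(1.96 − bias/1.147). Against a nominal 2.5%, it is 2.7% to 5.8% in the first row and 2.6% to 4.2% in the second. A simulation of the first row (40,000 trials per cell, correlation 0.6 between last-visit and 6-month change, LOCF then t-test) gave 2.7% to 5.6%.

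At the planned effect the sign turns toward the intervention when dc/di exceeds (Dc + 3.43)/Dc, which is 4.4, 2.7, 2.1 and 1.9 for Dc = 1, 2, 3 and 4.

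**2. Not a bound.** If intervention dropouts worsen by w points after their last visit while control dropouts hold steady, LOCF overstates benefit by di·w. For w = 2 to 6 this is 0.13 to 0.39 points with 3/46 missing, and 0.39 to 1.17 points (up to 1.0 SE) with 9/46 missing.

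**3. Coverage of data missing not at random (MNAR).** The chained-equations imputation conditions on baseline, group and observed follow-up, with no shift or reference-based step, so it assumes MAR. The per-protocol analysis drops the dropouts, and the change-score t-test ignores the intermediate visits. Both need stricter assumptions than the mixed model, not weaker ones. Comparing GEE with the mixed model adds no MNAR analysis.

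**4. How much non-random dropout would matter.** The shift in imputed intervention values that removes significance is (observed difference − critical difference)/(m/46), where m intervention participants are missing. The critical difference is t(0.975)·5.5·√(2/n), with n between 46−m and 46.

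| Missing | Critical difference | Tipping shift, observed 3.43 | Tipping shift, observed 3.0 |
|---|---|---|---|
| 3/46 | 2.28–2.36 | 16–18 | 10–11 |
| 5/46 | 2.28–2.42 | 9–11 | 5–7 |
| 9/46 | 2.28–2.55 | 4.5–6 | 2–4 |

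**The case against.** The strongest reply is that the illustration takes only improving controls. If controls are stable or worsen, the SAP's direction is right at the planned effect when control dropout is higher. With Dc = 0 the bias is −(1−f)·di·3.43 whatever the control dropout. With Dc = −1 or −2, f = 0.25 and 20% versus 5% dropout, it is −0.24 or −0.35. Even with improving controls, reversal at the planned effect needs control dropout roughly 2 to 4 times that of the intervention arm, not merely higher. All of this stands, and it confirms that the sign varies. Improving controls are also plausible, since the Protocol gives them regular clinic reviews and psychiatric referral where needed.

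The values of f are assumed, and dropout before month 1 (f = 0) is left out of the tables. Including it widens the no-effect maximum to 0.15 × 4 = 0.60 points (0.52 SE, 7.5%), which strengthens the point.

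LOCF is optional and secondary, the SAP does name non-random missingness, and it promises to examine dropout patterns and differences between the ITT and per-protocol results. That limits the harm, but none of it supplies an MNAR method. Finally, 4.6 does not say imputation is done only above 10%, so the commitment in 4.3 survives; the mismatch is one of wording.

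**Conclusion.** The concern holds. LOCF has no fixed direction of bias here and bounds nothing, and the SAP's supporting example is the case that can favour the intervention when controls improve. Apart from LOCF's no-change assumption, no specified analysis allows for MNAR dropout.

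The size is modest. At the implied 6.5% attrition, balanced between arms, the bias is zero with no effect and −0.08 to −0.17 points at the planned effect; it stays within 0.45 points over the tabulated range. At planned attrition and effect, a positive result would survive a shift of 16 to 18 points on a 27-point scale. With 9/46 missing and an observed difference of 3.0 the margin falls to 2 to 4 points. These sizes rest on assumed control trajectories, dropout splits and values of f; the error in the label does not. The primary mixed model is unaffected. The change should be made.

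**What to change.** - In section 4.3, delete the descriptions of LOCF as very conservative and as a worst-case bound, and the parenthetical about its direction. Do not use LOCF as a bound.
- State in both 4.3 and 4.6 that multiple imputation is run whatever the amount missing. The implied 6.5% attrition lies below the 10% trigger, so a reader of 4.6 alone might skip it.
- Add one delta-adjusted tipping-point analysis on those imputations. Worsen the imputed 6-month values in the intervention arm (PHQ-9 and FSS up, MMSE and Barthel Index down) in steps until significance is lost or the scale limit is reached, and report that delta. Do not fix a short grid, since the tipping value can run from about 2 to 18 PHQ-9 points in the cases above.

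Another MNAR method would also serve; this one reuses imputations already planned. The cost is SAP wording in two sections and one extra sensitivity analysis, with no new data and no change to the primary model.
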